6.2 Investigational device

6.2.1 Foliage Hydrofil

Foliage Hydrofil is a CE marked, class III, resorbable medical device (sterile, non-pyrogenic and physiological gel) to be used for the hydration of the skin and for the correction of superficial skin imperfections of the face and body and in the process of repairing the dermal tissue. The main component is HA sodium salt of non-animal origin, produced by bacterial fermentation, with a molecular weight similar to the human HA. Foliage Hydrofil does not contain human tissues or their derivatives.

Foliage Hydrofil is indicated for superficial cutaneous blemishes of the face or other body areas.

The medical device is formulated as injectable vials of 2 mL (1.6% HA formulation). In this clinical investigation each subject will receive three treatments, one vial 2mL each, with Foliage Hydrofil, 3 weeks apart. Foliage Hydrofil will be injected with 30G 4mm only. The area treated will be the face. The device administration could be done after an anesthetic cream application, according to Investigator's judgement.

6.2.1.1 Packaging and labelling

The Foliage Hydrofil will be provided for the study by the Sponsor of this clinical investigation.

The device shipment to the study site will be done only after the completion of Ethics and administrative procedures.

CONFIDENTIAL Page 20 of 51

The market packaging and labelling will be used. Only and additional label will be added to the outer box, specific for the clinical investigation.

Each package of treatment will contain:

- Instruction for use (IFU)
- 1 sealed blister containing 1 single-dose / single-use sterile pre-filled syringe (1x2 ml)
- adhesive labels to be applied on the clinical chart/patient card for product tracking
- 1 needle

6.2.1.2 Study device instructions for use

Foliage Hydrofil is intended for injection in the derma, for the hydration of the skin and the correction of skin blemishes, thanks to its HA content.

The device will be administered at clinical site by a qualified physician, already experienced with the use of similar devices. In any case specific instructions for the correct management of the study product will be provided by the Sponsor before the enrolment start. Product instructions for use (IFU) shall be fully complied.

Each treatment session will involve multiple microinjections, with needles 30G 4mm, in the face (external corner of the eye and cheek). The amount of product injected will be up to 2 mL, according to Investigator's judgement; the microinjections will be performed at a distance of 1–2 cm from each other.

An anesthetic cream could be used before injections, at Investigator's discretion.

The study product shall be carefully stored at the study site, in a safe area and separately from other devices/drugs/products. It shall be stored at room temperature (Min 2°C; Max 25°C), possibly in a dry and cool place, away from direct sunlight or heat.

6.2.1.3 Study product accountability and compliance

The Investigator is responsible for ensuring the accountability of the study product. Accountability records will include:

- confirmation of product delivery and receipt to/at the clinical site
- records concerning the product administration to each subject
- the return to the Sponsor or alternative disposition of unused products.

The Investigator should maintain records that adequately document:

CONFIDENTIAL Page 21 of 51

Version 1 date 02FEB2022

- that the subjects were treated with the quantities specified by the clinical investigation plan/amendment(s)
- that all study products provided by the Sponsor were fully reconciled.

Unused products must not be discarded or used for any purpose other than the present clinical investigation.

Subjects will be reminded of the importance of strictly complying with the instructions received from the Investigator.

Compliance to the treatment will be done through Investigator's records and vials accountability.

6.2.2 Concomitant Medications/Treatments

Any medication/treatment (other than those excluded by the clinical investigation plan) that is considered necessary for the subjects' well-being and does not interfere with the study product can be given/administered/prescribed at the Investigator's discretion.

The following prior and concomitant medications shall be avoided, as far as possible, during the study participation:

- any tissue augmenting therapy with non-permanent filler or treatment with botulinum toxin, aesthetic surgical therapy, laser treatment, mesotherapy, or any form of peeling in the face, or décolléte;
- use of injectable revitalization preparations:
- use of retinoic acid;
- treatment with permanent filling materials
- chemotherapy, immunosuppressive agents or corticoids;
- thrombolytics, anticoagulants, inhibitors of platelet aggregation
- sun exposure or tanning booths or UV sources (SPF 50+ should applied in case sun exposure cannot be avoided).

To be avoided close to the treatment, the intake of any treatment (aspirin, N.S.A.I.D., Vitamin E) acting on the fluidity of the blood, to minimize the possibility of bruising or bleeding of the injected area.

Any concomitant medication/treatment shall be recorded in the appropriate section of the eCRF.

CONFIDENTIAL Page 22 of 51

6.3 Subjects

In this clinical investigation 24 caucasian man and women of 30-55 years, with signs of skin aging in the face and fulfilling the following eligibility criteria will be enrolled.

Some eligibility criteria reflect the device contraindications/precautions and other criteria have the purpose of avoiding confounding factors that could interfere with study results.

6.3.1 Inclusion criteria

Subjects presenting all the following inclusion criteria will be eligible to enter the study:

- 1. Generally healthy man and women, aged between 30 and 55 years (inclusive), looking for aesthetic procedures to improve the aspect of their face.
- 2. Caucasian race (skin type from I to IV as per Fitzpatrick Skin Type scale);
- Visible signs of skin aging in the face (e.g. reduced skin elasticity, reduced turgor, actinic elastosis, smaller and larger wrinkles) according to the Investigators opinion;
- 4. Corneometer Capacitance of the area treated ≤ 80
- 5. Subjects wishing not to modify their lifestyle during the study period;
- Subjects with cooperative attitude, able to comprehend the full nature and the
 purpose of the investigation, including possible risks, side effects and discomforts
 and willing to adhere to the study schedule (including attendance to the planned
 visits) and study prescriptions;
- 7. Written informed consent release prior to any study-related procedures.

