6.4 Procedures

6.4.1 Study Visits and Assessments

Visit 1 screening – baseline- treatment start (day 1):

Subjects will be evaluated with regard to the inclusion and exclusion criteria that will allow their participation into the study.

Before any study specific evaluation is carried out, subjects will receive all the information about the study by the Investigator and will sign an informed consent form.

The following activities will be performed at first visit:

- Collection of demographic information
- Medical and surgical history
- Physical examination (focused on the skin)
- Previous (in the 30 days before) and concomitant medications / treatments recording
- Urine pregnancy test (where applicable)
- Inclusion/exclusion criteria assessment
- Photos of the treated area (before injections)
- Corneometer examination of treated area (before injections)
- Skin surface characteristics, texture, tone, fine lines and wrinkles (before injections)
- First treatment
- Local and systemic adverse events after the first treatment.

The following treatment session will be scheduled three weeks later, with a window of ± 4 days. The subject will be solicited to contact the Investigator for any problem between visits.

CONFIDENTIAL Page 25 of 51

Visit 2 (Day 21 ± 4) and Visit 3 (Day 42 ± 4):

The following activities will be done at Visit 2, and 3:

- Physical examination (focused on the skin)
- Change in concomitant medications / treatments recording
- Photos of the treated area (before second/third injection session)
- Corneometer examination of treated area (before second/third injection session)
- Skin surface characteristics, texture, tone, fine lines and wrinkles (before second/third injection session)
- PAIS Subject
- GAIS Investigator
- Second/third treatment
- Adverse events (occurred since previous visit) recording
- Local and systemic adverse events after the second/third treatment.

The second and third treatment sessions will be scheduled three weeks apart from each other, with a window of \pm 4 days. The subject will be solicited to contact the Investigator for any problem between visits.

The final visit will be scheduled about 2 months after last treatment session.

Visit 4 – End of study (Day 98 ±7):

The following activities will be done at Visit 4:

- Physical examination (focused on the skin)
- Change in concomitant medications / treatments recording
- Photos of the treated area
- Corneometer examination of treated area

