6.4.2 Corneometer assessment

Corneometer is one of the most popular measurement instrument to reproducibly and accurately determine the hydration level of the skin surface (stratum corneum).

The corneometer indicates the hydration level of the superficial layers of the skin via measurement of skin dielectric properties.

The measurements are performed by the application of a probe to the skin surface. Upon contact, an electric field passes through the stratum corneum and the dielectric constant is obtained.

The value of the dielectric constant (in arbitrary units) is directly proportional to the level of skin hydration.

On the probe head there is a fine piece of glass to ensure that only the capacitance changes due to water content are identified. Even small changes in water can be detected. The measurement time is short at only 1 second minimising occlusion effects. The depth of the measurement is 10-20µm, therefore limited to the stratum corneum, ensuring that deeper skin layers do not influence the measurement.

The measuring surface is around 49mm², so even small areas can be accurately measured.

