#### **9.1.1** Baseline Values

Data collected at Visit 1 (Day 1), before any study treatment administration, will be considered as baseline values.

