#### 13. DEVIATIONS FROM THE PROTOCOL SPECIFIED ANALYSIS

Waiting for EC approval (more than 6 months, due to Ethics Committee organization and procedures) and therefore for the start of the study, the centre purchased a new corneometer (fitted with an integrated sensor - average 50), with a capacitance algorithm based on a different scale from the one assumed when drafting the protocol.

The scale of the new corneometer is based on lower numbers, with normal values around 50 rather than around 100.

Therefore, after discussions with [name], it was decided that for skin hydration at corneometer, the subjects can be considering responders to the treatment when skin hydration increase is at least 7,5 from baseline to Day 98, using an absolute evaluation, instead of a percentage as hypothesized in the protocol drafting phase.

About the inclusion criterion n. 4 "Corneometer Capacitance of the area treated  $\leq$  80", [name] declares that the capacitance = 45 at new corneometer can be consider equivalent to capacitance = 80 at previous corneometer.

No other changes from the details specified in the study protocol have been included in this Statistical Analysis Plan (SAP).

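### The Visit 1 corneometer examination supplies both the entry cap and the baseline of an uncontrolled change endpoint, so if the cap excludes candidates, regression to the mean adds an apparent hydration gain whose size the documents do not fix

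*Protocol*

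**What the plan says.** - Protocol 6.3.1, criterion 4, admits a subject only with "Corneometer Capacitance of the area treated ≤ 80".
- SAP 13 reports that the centre bought a new instrument, "with normal values around 50 rather than around 100", and records a declaration that "capacitance = 45 at new corneometer can be consider equivalent to capacitance = 80 at previous corneometer".
- Protocol 6.4.1 and the flow-chart (Table 1) make Visit 1 the screening, baseline and first-treatment visit. One pre-treatment item is listed: "Corneometer examination of treated area (before injections". Protocol 6.1 instead places the first treatment on the day after the first visit. That wording should be reconciled, but under either reading only one pre-treatment examination is scheduled.
- SAP 9.1.1: "Data collected at Visit 1 (Day 1), before any study treatment administration, will be considered as baseline values".
- The study is single arm (Protocol synopsis). Protocol 7.3.5.1 and SAP 11.4.1 test the change from baseline to Day 98 by paired t-test or Wilcoxon signed rank test.
- Neither document mentions replicate readings, an untreated control area, adjustment for baseline, or regression to the mean.

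**The concern.** A corneometer value varies between occasions in the same person. An upper cap on one examination lets in some people whose value was low by chance on that day and keeps out some whose value was high by chance. When the same examination is then subtracted as baseline, the chance-low values tend to recover by Day 98, and the mean change is positive without any device effect. A control group under the same cap would show the same drift and cancel it, but this design has none.

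The primary objective is to evaluate and confirm an improvement in hydration, and the bias runs in that direction. A significant test against zero would mix any device effect with this shift. The responder proportion in SAP 11.4.2 (a rise of at least 7.5 by Day 98) uses the same baseline and inherits the problem.

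**Working it through.** **The plan's own figure.** Protocol 7.1 and SAP 7 assume a mean change of 7.5 with SD 8, alpha 0.05, 95% power and 20 evaluable subjects. The standardised effect is 7.5/8 = 0.9375. A two-sided paired t-test (sidedness is not stated; two-sided is assumed throughout) needs 17 subjects (power 95.2%), and 20 give 97.8%. Dividing 17 by the worst-case Wilcoxon efficiency gives 17/0.864 = 19.7, so 20. The sample size is adequate, and the issue is what the test measures.

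**Inputs**
- Cap c = 45 on the new device (SAP 13).
- Candidate mean μ: not in the documents. Assumed 40 to 50, then 30 to 35.
- Total SD of a reading σ: not in the documents. Assumed 8 to 12.
- Within-subject SD w: not in the documents. If the planned SD of change is all within-subject noise, w = 8/√2 = 5.66, about 5.7. SAP 7 repeats 7.5 and 8 unchanged although the scale has changed. Rescaled by SAP 13's equivalence, w = 5.66 × 45/80 = 3.18, about 3.2. The ratio of the two normal values would give 5.66 × 50/100 = 2.8.

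**Formulas.** For normal readings selected on X ≤ c, with z = (c − μ)/σ:
- share of candidates eligible = Φ(z)
- expected change with no device effect = (w²/σ) × φ(z)/Φ(z)
- chance of a false significant gain at n = 20: upper tail of the noncentral t with 19 df beyond 2.093, noncentrality = shift / (√2·w/√20)

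**Top of the main range** (μ = 50, σ = 8, w = 3.2): z = −0.625 and φ/Φ = 1.234. Shift = (10.24/8) × 1.234 = 1.58. Noncentrality = 1.58/(4.53/4.47) = 1.56, and the false-gain chance is 32%.

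**Bottom of the main range** (μ = 40, σ = 12, w = 3.2): z = 0.417 and φ/Φ = 0.553. Shift = (10.24/12) × 0.553 = 0.47. Noncentrality is 0.47, and the chance is 6%.

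Each cell below gives the value at σ = 8, then at σ = 12.

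| μ | Eligible | Shift, w = 3.2 | False gain | Shift, w = 5.7 | False gain |
|---|---|---|---|---|---|
| 50 | 27%, 34% | 1.58, 0.92 | 32%, 14% | 5.01, 2.93 | 75%, 34% |
| 45 | 50%, 50% | 1.02, 0.68 | 16%, 9% | 3.24, 2.16 | 40%, 21% |
| 40 | 73%, 66% | 0.57, 0.47 | 8%, 6% | 1.82, 1.50 | 16%, 12% |
| 35 | 89%, 80% | 0.26, 0.30 | 4%, 5% | 0.83, 0.96 | 6%, 7% |
| 30 | 97%, 89% | 0.09, 0.17 | 3%, 4% | 0.29, 0.55 | 4%, 5% |

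The nominal chance of a significant result in the favourable direction is 2.5%. The 75% corner implies a visit-to-visit correlation of 1 − 32.5/64, about 0.5. A simulation there that also lets selection narrow the spread of the changes gives about 83%, so 75% is not an overstatement of that corner.

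**Responders.** In the same corner about 36% of untreated subjects would pass the 7.5 threshold, against 1 − Φ(7.5/8), about 17%, without selection.

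**The case against.** The strongest reply is that the size is unknown and may be trivial. SAP 13 gives a normal value of about 50, which is not the mean of the people screened. Criterion 3 requires visible signs of skin aging, so candidates may sit well below normal and nearly all may pass the cap. This stands, and the last two rows of the table show the effect fading to near nominal.

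Two further points stand in part.
- Taking 5.7 as within-subject SD attributes the whole planned SD of change to noise and carries a figure planned on the old scale over to the new one. True variation in response would make it too large. It cannot be excluded, because SAP 7 restates 8 without rescaling, but it belongs in the worst case.
- The documents schedule an examination over the treated areas without saying how many probe readings it comprises. Averaging several would shrink the measurement-error part of the shift, though not the day-to-day part.

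A reader might infer that a cap of 45 cuts deep into the candidate distribution because normal is about 50, or that the artefact could account for the planned 7.5 units. The documents support neither inference: the first needs a candidate mean they do not give, and with the new-device cap even the worst corner examined stops near 5 units.

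What the reply leaves untouched is the structure. If the cap excludes anyone and readings are not perfectly correlated between visits, the expected change is positive, and nothing in the design or analysis removes it.

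**Conclusion.** The point holds as a conditional bias. Under cap 45, candidate mean 40 to 50, total SD 8 to 12 and within-subject SD 3.2, the expected spurious gain is about 0.5 to 1.6 units, which is 6% to 21% of the planned 7.5 (0.47/7.5 and 1.58/7.5). The false-gain chance is about 6% to 32%. With a candidate mean of 30 to 35 and either within-subject SD, it is about 0.1 to 1.0 units and 3% to 7%. The worst case, about 5 units and 75%, needs mean 50, total SD 8 and the unscaled within-subject SD of 5.7 together. All of this assumes normal readings and equal within-subject SD at both visits.

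It would go too far to say that the trial will succeed with an inert product. The supportable conclusion is that a p-value below 0.05 against zero cannot by itself be read as a device effect.

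**What to change.** **1. Analysis, before database lock.** SAP 2 says the plan is finalised before lock, so this is still open. In SAP 11.4.1 add a sensitivity analysis that reports the primary mean change with its 95% CI beside the same change minus the regression-to-the-mean shift, over a stated range of candidate mean, total SD and within-subject SD. State that a significant test against zero is not on its own evidence of a device effect if the lower confidence limit does not exceed the plausible shift. Keep this as interpretation: a new success criterion at this stage would alter the primary decision rule late. Put the same caveat on the responder proportion in SAP 11.4.2. The Screening/Enrolment Log (Protocol 6.1) records reasons for not entering the study. The share refused on criterion 4 estimates 1 − Φ(z) and would narrow the range.

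**2. Conduct, only if Visit 1 can still be changed.** SAP 4.2 and SAP 7 describe treatment and recruitment in the past tense, so this is probably too late for the present cohort. Otherwise, in Protocol 6.4.1, use one reading for criterion 4 and a separate, later pre-injection set, averaged, as baseline. Protocol 6.4.2 notes that "The measurement time is short at only 1 second", so the added time is small. Do not also subtract a shift estimated from those same-day replicates: they measure only the component that the separate baseline has already removed.

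**Cost.** One additional table, plus a few seconds of probe time if step 2 is possible. Same-day repeats leave day-to-day variation in place. If half of the within-subject variance is same-day error (an assumption), a separate baseline halves the shift. The correction in step 1 rests on assumed SDs, and the reported effect may look slightly less favourable.

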6.3.2 Exclusion criteria

Subjects presenting one or more of the following exclusion criteria will not be eligible to enter the study:

- 1. Pregnancy or breastfeeding woman or woman of childbearing potential not practicing adequate contraception.
- 2. Subjects with Fitzpatrick skin type from V to VI
- 3. Subjects with known allergy/hypersensitivity to product components.

CONFIDENTIAL Page 23 of 51

- 4. Extensively photo damaged and aged skin according to the Investigators opinion.
- Active skin disease, inflammation or related conditions, such as infection, perioral dermatitis, seborrheic eczema and rosacea in the face, hands or décolletage.
- 6. Immune system disorders
- 7. History of or active collagenosis (e.g. systemic lupus, erythematosis, rheumatic arthritis, skin or systemic sclerosis).
- 8. Concomitant therapy with thrombolytics or anticoagulants, or have taken inhibitors of platelet aggregation, within 2 weeks before the first product administration.
- 9. Tattoo/s on the skin around the treatment site
- 10. History of cancerous or pre-cancerous lesions in the face, neck and décolletage.
- 11. Previous tissue augmenting therapy with non-permanent filler or treatment with botulinum toxin, aesthetic surgical therapy, laser treatment, mesotherapy, or any form of peeling in the face, hands or décolletage within 12 months prior to the baseline visit.
- 12. Use of injectable revitalization preparations within 12 months prior to the baseline visit.
- 13. Use of retinoic acid within 6 months prior to the baseline visit.
- 14. Previous or concomitant treatment with chemotherapy, immunosuppressive agents or corticoids.
- 15. History of treatment with permanent filling materials.
- 16. Participation in any other clinical study within 30 days prior to the first visit or plan to participate in another clinical study during this study period.
- 17. Planned or ongoing weight reduction program during the study.
- 18. Known history of drug or alcohol abuse within 6 months prior to the baseline visit.
- 19. Known hypersensitivity to one or more components of anesthetic creams
- 20. Nicotine use during the study or stopped within 12 months before the first visit.

CONFIDENTIAL Page 24 of 51

- 21. Any medical condition that in the opinion of the Investigator makes the subject unsuitable for inclusion (e.g. severe chronic disease, malignancy, bleeding disorder, skin diseases etc).
- 22. Other condition preventing the subject to entering the study in the Investigator's opinion e.g. subjects anticipated to be unreliable, unable to return for the follow-up visits, not likely to avoid other prohibited treatments or procedures or incapable of understanding the information or instructions.

6.4 Procedures

6.4.1 Study Visits and Assessments

Visit 1 screening – baseline- treatment start (day 1):

Subjects will be evaluated with regard to the inclusion and exclusion criteria that will allow their participation into the study.

Before any study specific evaluation is carried out, subjects will receive all the information about the study by the Investigator and will sign an informed consent form.

The following activities will be performed at first visit:

- Collection of demographic information
- Medical and surgical history
- Physical examination (focused on the skin)
- Previous (in the 30 days before) and concomitant medications / treatments recording
- Urine pregnancy test (where applicable)
- Inclusion/exclusion criteria assessment
- Photos of the treated area (before injections)
- Corneometer examination of treated area (before injections)
- Skin surface characteristics, texture, tone, fine lines and wrinkles (before injections)
- First treatment
- Local and systemic adverse events after the first treatment.

The following treatment session will be scheduled three weeks later, with a window of ± 4 days. The subject will be solicited to contact the Investigator for any problem between visits.

CONFIDENTIAL Page 25 of 51

Visit 2 (Day 21 ± 4) and Visit 3 (Day 42 ± 4):

The following activities will be done at Visit 2, and 3:

- Physical examination (focused on the skin)
- Change in concomitant medications / treatments recording
- Photos of the treated area (before second/third injection session)
- Corneometer examination of treated area (before second/third injection session)
- Skin surface characteristics, texture, tone, fine lines and wrinkles (before second/third injection session)
- PAIS Subject
- GAIS Investigator
- Second/third treatment
- Adverse events (occurred since previous visit) recording
- Local and systemic adverse events after the second/third treatment.

The second and third treatment sessions will be scheduled three weeks apart from each other, with a window of \pm 4 days. The subject will be solicited to contact the Investigator for any problem between visits.

The final visit will be scheduled about 2 months after last treatment session.

Visit 4 – End of study (Day 98 ±7):

The following activities will be done at Visit 4:

- Physical examination (focused on the skin)
- Change in concomitant medications / treatments recording
- Photos of the treated area
- Corneometer examination of treated area
- Skin surface characteristics, texture, tone, fine lines and wrinkles
- PAIS Subject
- GAIS Investigator
- Overall satisfaction by subject
- Adverse events (occurred since previous visit) recording.

Should the subject interrupt or conclude in advance the clinical study, for any reason, a Visit 4 will be completed.

CONFIDENTIAL Page 26 of 51

